**This document is confidential.**

with their randomized study medication for an evaluation of treatment adherence. Subjects will undergo a measurement of height, weight, HR, BCVA measurement (distance and near), photopic pupil size measurement, SLE, tonometry, dilated fundus examination, cycloplegic autorefraction, axial length, and, if possible, crystalline lens thickness. Sites will update concomitant medications, conduct AE assessment, and perform treatment adherence assessment.

Every effort should be made to keep subjects in the study and conduct all study visits as scheduled. If a subject is discontinued from study medication before the Month 48 visit, then all Month 48 (EOS) procedures should be performed at the visit the subject is discontinued.

Full details of each visit can be found in Table 2: Schedule of Procedures in the protocol.

This document is confidential.

## 4. Endpoints

### 4.1. Primary Efficacy Endpoint

The primary efficacy endpoint is the overall between-treatment group (Atropine Sulfate Ophthalmic Solution, 0.02% versus Vehicle) difference in the proportion of subjects' eyes who show less than 0.5 D myopia progression (SER) from baseline at the Month 36 visit.

### 4.2. Secondary Efficacy Endpoints

The secondary efficacy endpoints will consist of:

1. Between-treatment group (Atropine Sulfate Ophthalmic Solution, 0.02% versus Vehicle) difference in the mean change from baseline in SER at the Month 36 visit.
2. Between-treatment group (Atropine Sulfate Ophthalmic Solution, 0.01% versus Vehicle) difference in the proportion of subjects' eyes who show less than 0.5 D myopia progression (SER) from baseline at the Month 36 visit.
3. Between-treatment group (Atropine Sulfate Ophthalmic Solution, 0.01% versus Vehicle) difference in the mean change from baseline in SER at the Month 36 visit.
4. Between-treatment group (Atropine Sulfate Ophthalmic Solution, 0.02% versus Vehicle) difference in the mean change from baseline in axial length at the Month 36 visit.
5. Between-treatment group (Atropine Sulfate Ophthalmic Solution, 0.01% versus Vehicle) difference in the mean change from baseline in axial length at the Month 36 visit.

### 4.3. Tertiary Endpoints

Tertiary endpoints will consist of:

1. Between-treatment group (Atropine Sulfate Ophthalmic Solution, 0.02% versus Vehicle) difference in the proportion of subjects' eyes who show less than 0.5 D myopia progression (SER) from baseline at the Month 24 and Month 12 visits.
2. Between-treatment group (Atropine Sulfate Ophthalmic Solution, 0.02% versus Vehicle) difference in the mean change from baseline in SER at the Month 24 and Month 12 visits.
3. Between-treatment group (Atropine Sulfate Ophthalmic Solution, 0.01% versus Vehicle) difference in the proportion of subjects' eyes who show less than 0.5 D myopia progression (SER) from baseline at the Month 24 and Month 12 visits.
4. Between-treatment group (Atropine Sulfate Ophthalmic Solution, 0.01% versus Vehicle) difference in the mean change from baseline in SER at the Month 24 and Month 12 visits.
5. Between-treatment group (Atropine Sulfate Ophthalmic Solution, 0.02% versus Vehicle) difference in the proportion of subjects' eyes who show less than 0.75 D myopia progression (SER) from baseline at the Month 36 visit.
6. Between-treatment group (Atropine Sulfate Ophthalmic Solution, 0.01% versus Vehicle) difference in the proportion of subjects' eyes who show less than 0.75 D myopia progression (SER) from baseline at the Month 36 visit.

This document is confidential.

7. Between-treatment group (Atropine Sulfate Ophthalmic Solution, 0.02% versus Vehicle) difference in the time to change from baseline in myopia of -0.75 D SER.
8. Between-treatment group (Atropine Sulfate Ophthalmic Solution, 0.01% versus Vehicle) difference in the time to change from baseline in myopia of -0.75 D SER
9. Between-treatment group (Atropine Sulfate Ophthalmic Solution, 0.02% versus Vehicle) difference in the mean number of new prescriptions given after the start of treatment due to progression through the Month 36 visit.
10. Between-treatment group (Atropine Sulfate Ophthalmic Solution, 0.01% versus Vehicle) difference in the mean number of new prescriptions given after the start of treatment due to progression through the Month 36 visit.
11. Between-treatment group (Atropine Sulfate Ophthalmic Solution, 0.02% versus Vehicle) difference in the proportion of subjects who progressed from baseline to high myopia (SER -6.00 D or more myopic) at the Month 36 visit.
12. Between-treatment group (Atropine Sulfate Ophthalmic Solution, 0.01% versus Vehicle) difference in the proportion of subjects who progressed from baseline to high myopia (SER -6.00 D or more myopic) at the Month 36 visit.
13. Interaction between demographic variables (age 6 – 8 years versus 9 – 10 years; baseline SER - 0.50 to -3.00 D versus more myopic than -3.00 D SER; Asian versus non-Asian; dark irides versus light irides, region (U.S. versus E.U.); female versus male and SER at randomization.
14. Between-treatment group (Atropine Sulfate Ophthalmic Solution, 0.02% versus Vehicle) difference in the change from baseline in crystalline lens thickness at the Month 36 visit.
15. Between-treatment group (Atropine Sulfate Ophthalmic Solution, 0.01% versus Vehicle) difference in the change from baseline in crystalline lens thickness at the Month 36 visit.

#### **4.4. Exploratory Efficacy Endpoints**

Exploratory endpoints will consist of:

1. Between-treatment group difference in the mean change from study baseline in SER at the Month 48 visit for all subjects who respond in the Atropine Sulfate Ophthalmic Solution treatment groups at the Month 36 visit.
2. Between-treatment group difference in the mean change from Stage 2 baseline (Month 36) in SER at the Month 48 visit for all subjects who respond in the Atropine Sulfate Ophthalmic Solution treatment groups at the Month 36 visit.
3. Between-treatment Group (Atropine Sulfate Ophthalmic Solution, 0.02% versus Vehicle and Atropine Sulfate Ophthalmic Solution, 0.01% versus Vehicle) Difference in the Proportion of Subjects' Eyes with Higher Myopia (SER  $\leq$  -3.00) who Show less than 0.75 D Myopia Progression (SER) From Baseline at the Month 36 Visit

This document is confidential.

## **5. Analysis Sets**

### **5.1. Enrolled Set**

The Enrolled Set will include all subjects enrolled. Unless specified otherwise, this set will be used for subject listings and summaries of subject disposition.

### **5.2. Safety Set**

The Safety Set (SS) will include all subjects who were administered at least one dose of study medication for a given stage. Stage 1 Safety Set is defined by administration of at least one dose of study medication in Stage 1. Stage 2 Safety Set is defined by administration of at least one dose of study medication in Stage 2. Subjects will be analyzed according to first treatment received for each stage. In the case of listings or tables that present data from both stages, then treatment sequence will be used. The SS will be used for all analyses of safety endpoints and for the presentation of subjects in all subject listings.

### **5.3. Intent-to-Treat Set**

The Intent-to-Treat (ITT) Set will include all randomized subjects for a given stage. Stage 1 ITT Set is defined by randomization of a subject into a Stage 1 treatment. Stage 2 ITT Set is defined by randomization of a subject into a Stage 2 treatment. Subjects will be analyzed according to randomized treatment. The ITT Set will be used for all analyses of efficacy endpoints, unless otherwise specified, and for the presentation of subjects in all subject listings.

### **5.4. Modified Intent-to-Treat**

The Modified Intent-to-Treat (mITT) Set will include all randomized subjects, for a given stage, aged 6 to 10 years at the time of randomization in Stage 1. Stage 1 mITT Set is defined by randomization of a subject, aged 6 to 10 years at the time of randomization in Stage 1, into a Stage 1 treatment. Stage 2 mITT Set is defined by randomization of a subject, aged 6 to 10 years at the time of randomization in Stage 1, into a Stage 2 treatment. This will be the population for the primary efficacy analyses. Subjects will be analyzed according to randomized treatment.

### **5.5. Per Protocol Set**

The Per Protocol Set (PPS) will include all subjects who remain in the study through end of stage and have no major or critical protocol violations. Stage 1 PPS requires subjects to remain in the study through Month 36. Stage 2 PPS requires subjects to remain in the study through Month 48. This will be the population for selected efficacy analyses. Subjects will be analyzed according to randomized treatment. Criteria for inclusion in the PPS includes the following important Protocol deviations for which subjects are to be included within each analysis set are determined at a BDRM (see 5.7) before unblinding.

### **5.6. Modified Per Protocol Set**

The Modified Per Protocol Set (mPPS) will include all subjects in the PP analysis population in each stage who were aged 6 to 10 years at the time of randomization. This will be the population for selected efficacy analyses. Subjects will be analyzed according to randomized treatment.

### **5.7. Protocol Deviations**

Protocol deviations will be collected throughout the study. All protocol deviations classified as Minor, Major, or Critical. Based on these classifications, subjects with Major or Critical deviations will be tentatively

This document is confidential.

identified as not in the PPS and Modified PPS. Listings of proposed analysis set designations and protocol deviations will be distributed to the sponsor for review.

Protocol deviations and analysis set assignments will be reviewed during a Masked Data Review Meeting (BDRM). Additional details of selection criteria, documentation, and scheduling of the BDRM to be provided for review will be described in the BDRM Preparation Plan.

This document is confidential.

## 6. General Aspects for Statistical Analysis

### 6.1. General Methods

- SAS® version 9.4 or newer is to be used for all analyses and outputs
- Unless otherwise specified, summaries will be presented for each treatment group by study stage
- Continuous variables will be summarized using the number of observations (n), mean, standard deviation (SD), median, minimum, and maximum. Due to the expected strong correlation between eyes within a subject, eye-related continuous variables, where the object of measure is subjects' eyes, will be summarized using the number of observations (n), mean, Inter Quartile Range (IQR), median, minimum, and maximum. Categorical variables will be summarized using number of observations (n), frequency, and percentages of subjects.
- All relevant subject data will be included in listings. All subjects entered into the database will be included in subject data listings.

### 6.2. Key Definitions

Treatment-emergent adverse events (TEAEs) of Stage 1 are defined as any new or worsening of existing adverse events that occur or worsen between the first dose date of Stage 1 and the last dose date of Stage 1.

TEAEs of Stage 2 are defined as any AE the occurs or worsens between the first dose date of Stage 2 and the last dose date of Stage 2.

First dose date for Stage 1 is defined as the first dose of study medication received after randomization in Stage 1.

First dose date for Stage 2 is defined as the first dose of study medication received after the Stage 1 last dose date and subject is re-randomized.

For subjects who did not receive study medication in a given stage, leave first dose date for that stage as missing. If the first dose date is missing and if the subject is randomized, impute the missing first dose date using the randomization date in the analysis of Time to Change from Baseline in Myopia Progression of -0.75D (see 8.3.7 and 8.3.8).

Baseline for Stage 1 is defined as the last measurement prior to first dose of study medication in Stage 1, If an adverse event starts or non-study medication taken on the day of first dose it will be treated as occurring after treatment started. All other planned measurements are presumed to occur prior to first dose of study medication.

Baseline for Stage 2 will be defined as latest results prior to start of study medication in Stage 2, which occurs the day after the Month 36 visit. The results of the Month 36 visit will act as the baseline for Stage 2.

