#### Treatment arms are:

- Atropine Sulfate Ophthalmic Solution, 0.01%
- Atropine Sulfate Ophthalmic Solution, 0.02%
- Vehicle (placebo)

Both eyes will be treated; myopia must be bilateral to qualify. If myopia is unilateral at screening or the child seems likely to cross the threshold for bilateral myopia of at least -0.50 SER, the subject can be asked to return while the enrollment period is still open to determine his or her eligibility. Subjects will return to the clinical site at 6-month intervals for 3 years to undergo a series of safety and efficacy evaluations and at 3-month intervals throughout the study for update of concomitant medications and adverse event (AE) assessment. While it is preferred that the subject attend every visit, the parent/guardian may attend a 3-month visit without the subject if necessary; both the subject and their parent/guardian must be present for all 6-month visits. At each study visit, unopened/unused and used study medication materials will be returned, concomitant medications will be updated, AE assessment will be conducted, allocated study medication will be dispensed for the next 3-month study period, and treatment adherence assessment will be performed.

Site staff will also contact subjects or their parents/guardians by telephone at the end of Month 1 and Month 2 and then midway between office visits during the initial year of the study to collect information regarding AEs and treatment adherence. Telephone checks can be continued or reinstated at any time during the study to assist with maintaining protocol and treatment adherence.

After a subject completes all safety and efficacy assessments at Month 36 (the primary efficacy time point) the randomized cross-over stage (Stage 2) will commence, and each subject will be re randomized to receive 1 of the 3 study medications for the final year of the study. Subjects randomized to either 0.01% or 0.02% Atropine Sulfate Ophthalmic Solution during Stage 1 will be re randomized to treatment with Atropine Sulfate Ophthalmic Solution, 0.01%, Atropine Sulfate Ophthalmic Solution, 0.02%, or Vehicle, and subjects randomized to the Vehicle group in Stage 1 will be re-randomized to active treatment with Atropine Sulfate Ophthalmic Solution, 0.01% or Atropine Sulfate Ophthalmic Solution, 0.02%. In Stage 2, study medication will be administered one drop in each eye QD at bedtime, as before, for 1 year.

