## **Early Termination Visits**

Every effort should be made to keep subjects in the study and conduct all study visits as scheduled. If a subject is discontinued from study medication before the Month 48 visit, then all Month 48 (EOS) procedures should be performed at the visit the subject is discontinued.

If a subject is off study medication and is being followed for safety assessments then an EOS Month 36 visit should be completed, as these subjects will not continue on to Stage 2.

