# Withdrawal of Subjects:

All subjects randomized into the study will be encouraged to complete all study assessments through the Month 48 Visit (End of Study), including subjects that cannot or do not wish to continue study treatment (withdraw consent/assent from study treatment but are willing to continue study visits).

The following are the criteria for considering withdrawal from the study (Study discontinuation prior to Visit Month 48):

- Withdrawal of subject consent/assent to continue with study visits.
- If the site and/or the overall study is terminated for any reason.
- The Investigator considers it is in the best interest for the subject to leave the study. This may include the development of damage to the cornea (Section 8.5 Discontinuation of Study Medication).

If a subject withdraws from the study, the reason for the subject's withdrawal will be recorded in the electronic case report form (eCRF).

If a subject is discontinued from study medication before the Month 48 visit, then all Month 48 procedures should be performed at the visit the subject discontinues study medication. The subject should continue in the study off study medication. Subjects should be encouraged to return for the 6 Month interval visits; however, returning for the 12 Month interval visits is essential. Subjects discontinuing study medication prior to Month 36 would continue to be seen for scheduled visits (at 6 Month or 12 Month intervals as noted above) until they reach the Month 36 interval.

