### 9.3. Adverse Events

The analysis of AEs will be based on the concept of treatment-emergent AEs (TEAEs). An adverse event is any untoward medical occurrence associated with the use of a drug in humans, whether or not considered drug-related.

Treatment-emergent adverse events (TEAEs) of Stage 1 are defined as any new or worsening of existing adverse events that occur or worsen between start (or increase in intensity on or after the first dose date

This document is confidential.

of Stage 1 treatment on day 1) and the last dose date of Stage 1. TEAEs of Stage 2 are defined as any AE that occurs or worsens between the first dose date of Stage 2 and the last dose date of Stage 2.

The first dose date for Stage 1 is defined as the first dose of study medication received after randomization in Stage 1. The first dose date for Stage 2 is defined as the first dose of study medication received after the Stage 1 last dose date and subject is re-randomized. All adverse events (AEs) will be coded using the MedDRA version 20.1 or higher. The following listings of AEs will be provided by Stage and subjects:

- All AEs,
- Serious adverse events (SAEs) Serious ocular and non-ocular AEs, respectively
- All deaths
- TEAEs (overall, ocular, non-ocular, respectively) leading to study withdrawal
- TEAEs (overall, ocular, non-ocular, respectively) leading to study drug discontinuation
- Severe AEs
- Study drug related AEs
- Study drug related SAEs

Treatment-emergent adverse events will be included in summary tables by treatment received for each stage. Ocular TEAEs will be summarized separately from all other TEAEs. An overall summary table of TEAEs for each stage will be produced for the following categories:

- Any Ocular TEAE
- Severe Ocular TEAEs
- Study drug-related Ocular TEAEs
- Serious Ocular TEAEs
- Study drug-related Serious Ocular TEAEs
- Ocular TEAEs leading to study discontinuation
- Ocular TEAEs leading to death
- Any Non-Ocular TEAE
- Severe Non-Ocular TEAEs
- Study drug-related Non-Ocular TEAEs
- Serious Non-Ocular TEAEs
- Study drug-related Serious Non-Ocular TEAEs
- Non-Ocular TEAEs leading to study discontinuation
- Non-Ocular TEAEs leading to death

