	14.2.4.7.3.2	Summary of the Change from Stage 2 Baseline in Normalized SER (D) in Stage 2 by Stage 1 to Stage 2 Treatment Description and Visit (Asian vs. Non-Asian)	Stage 2 Intent-to-Treat Set
	14.2.4.7.4.1	Summary of the Change from Stage 2 Baseline in Normalized SER (D) in Stage 2 by Stage 1 to Stage 2 Treatment Description and Visit (Dark Irides vs. Light Irides)	Stage 2 Modified Intent-to-Treat Set
	14.2.4.7.4.2	Summary of the Change from Stage 2 Baseline in Normalized SER (D) in Stage 2 by Stage 1 to Stage 2 Treatment Description and Visit (Dark Irides vs. Light Irides)	Stage 2 Intent-to-Treat Set

This document is confidential.

Header	Table Number	Name	Analysis Set
	14.2.4.7.5.1	Summary of the Change from Stage 2 Baseline in Normalized SER (D) in Stage 2 by Stage 1 to Stage 2 Treatment Description and Visit (U.S. vs. E.U.)	Stage 2 Modified Intent-to-Treat Set
	14.2.4.7.5.2	Summary of the Change from Stage 2 Baseline in Normalized SER (D) in Stage 2 by Stage 1 to Stage 2 Treatment Description and Visit (U.S. vs. E.U.)	Stage 2 Intent-to-Treat Set
	14.2.4.7.6.1	Summary of the Change from Stage 2 Baseline in Normalized SER (D) in Stage 2 by Stage 1 to Stage 2 Treatment Description and Visit (Female vs. Male)	Stage 2 Modified Intent-to-Treat Set
	14.2.4.7.6.2	Summary of the Change from Stage 2 Baseline in Normalized SER (D) in Stage 2 by Stage 1 to Stage 2 Treatment Description and Visit (Female vs. Male)	Stage 2 Intent-to-Treat Set
14.2.4.8		Change from Stage 2 Baseline in Crystalline Lens Thickness (mm) in Stage 2	
	14.2.4.8.1	Summary of the Change from Stage 2 Baseline in Crystalline Lens Thickness (mm) in Stage 2 by Stage 1 to Stage 2 Treatment Description and Visit	Stage 2 Modified Intent-to-Treat Set
	14.2.4.8.2	Summary of the Change from Stage 2 Baseline in Crystalline Lens Thickness (mm) in Stage 2 by Stage 1 to Stage 2 Treatment Description and Visit	Stage 2 Intent-to-Treat Set
14.3		Safety Data Summary Tables	
14.3.1		Adverse Events	
	14.3.1.1.1	Overall Summary of Treatment-Emergent Adverse Events - Stage 1	Stage 1 Safety Set
	14.3.1.1.2	Overall Summary of Treatment-Emergent Adverse Events - Stage 2	Stage 2 Safety Set
	14.3.1.2.1.1	Treatment-Emergent Adverse Events by System Organ Class and Preferred Term - Stage 1	Stage 1 Safety Set
	14.3.1.2.1.2	Ocular Treatment-Emergent Adverse Events by System Organ Class and Preferred Term - Stage 1	Stage 1 Safety Set

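### Adverse-event summaries stop on the last dose date with no lag, so a next-morning reaction to a final dose and events starting after early drug discontinuation get no count by arm

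*SAP*

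**What the plan says.** **Window.** SAP 6.2 defines Stage 1 treatment-emergent adverse events (TEAEs) as new or worsening events that "occur or worsen between the first dose date of Stage 1 and the last dose date of Stage 1". SAP 9.3 words the start of the window differently but ends it on the same date. The Stage 2 window likewise ends on the last Stage 2 dose date. No lag is given for either stage.

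**What is tabulated.** SAP 9.3 states: "Treatment-emergent adverse events will be included in summary tables by treatment received for each stage". The table index follows suit, beginning with "Overall Summary of Treatment-Emergent Adverse Events - Stage 1". Events outside the window appear in subject listings.

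**Who stays in follow-up.** On a child who stops drug, the Protocol synopsis (Withdrawal of Subjects) says: "The subject should continue in the study off study medication". It adds: "Subjects discontinuing study medication prior to Month 36 would continue to be seen for scheduled visits". Those visits are at 6- or 12-month intervals until Month 36, and only the 12-month ones are called essential. Early Termination Visits gives safety as a purpose: "If a subject is off study medication and is being followed for safety assessments then an EOS Month 36 visit should be completed". These children do not enter Stage 2. The Methodology text plans that at each study visit "concomitant medications will be updated, AE assessment will be conducted".

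**Serious events.** SAP 9.3 plans listings of serious adverse events (SAEs) with no TEAE restriction. The indexed serious-event listings, 14.3.2.2.1 (ocular) and 14.3.2.2.2 (non-ocular), are titled as treatment-emergent.

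**The concern.** Safety over the 3-year placebo-controlled stage is part of the primary objective. A window that closes on the calendar date of a bedtime dose leaves almost no time for a reaction to that dose to be recorded inside it. The Protocol also keeps children under observation after they stop drug and calls this safety follow-up, yet the SAP provides no adverse-event incidence by arm for that period. A reader of the safety tables could not tell whether events after stopping were balanced across arms without counting them by hand from listings. A reader who goes to the serious-event listings would find fewer events than SAP 9.3 says will be there.

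**Working it through.** No stated sample size, power or alpha figure is in dispute. The check sets the sections side by side, with simple counts and date arithmetic.

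**1. Final dose.** Let L be the last dose date. The rule requires onset or worsening on or before L, so an event first dated L + 1 is not a TEAE. Dosing is at bedtime (Protocol Methodology; SAP 3.7). The only clock times given are the Stage 2 e-diary entry hours, 6:00 PM to 11:45 PM. If the drop is given when logged, the time left on date L runs from 6 hours (6:00 PM to midnight) down to 0.25 hours (11:45 PM to midnight). Stage 1 clock hours are not given, so this is an illustration.

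**2. Are off-drug events counted elsewhere?**
- SAP 9.3 detailed summaries: 13 types × 3 (all, ocular, non-ocular) = 39, all TEAE.
- SAP 9.3 overall summary: every category is TEAE.
- Index 14.3.1: 13 types × 3 × 2 stages = 78, plus 2 overall summaries = 80, all TEAE.
- Index 14.3.2: 1 deaths + 2 serious + 3 drug discontinuation + 3 study withdrawal = 9 listings, of which 8 are TEAE-only. Deaths is the exception.
- Listing 16.2.7.1 holds all adverse events, so none is lost from the report.

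**3. Days outside the window, per child.** The scheduled days come from SAP Table 1 (Month 36 = Day 1096). Off-drug days = 1096 − scheduled day of stopping.

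| Stop at | Off-drug days | Share of 1,096 |
|---|---|---|
| Month 6 (Day 182) | 914 | 83.4% |
| Month 12 (Day 365) | 731 | 66.7% |
| Month 18 (Day 548) | 548 | 50.0% |
| Month 24 (Day 731) | 365 | 33.3% |
| Month 30 (Day 913) | 183 | 16.7% |

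These are examples for stops at scheduled six-month visits. A child can stop at any time, so they are not limits.

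**4. Across the trial.** The documents give no drug-stopping rate. The Protocol's 27% over 3 years is study drop-out, and drop-outs leave follow-up. As a pure scenario, suppose a constant share r stops per year and all stay to Month 36. Off-drug years per child = 3 − [1 − (1 − r)³] / [−ln(1 − r)]. For r = 2%, 5% and 10% this gives 0.089, 0.219 and 0.428 years, or 3.0%, 7.3% and 14.3% of three years. For 483 children that is about 43, 106 and 207 of 3 × 483 = 1,449 person-years. This is observation time, not a number of events, and the 10% case borrows the approximate annual drop-out rate only for scale.

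**5. Serious events.** Take an SAE that starts after the window, is not fatal and is judged unrelated. It is outside 14.3.2.2.1 and 14.3.2.2.2 (TEAE only), 14.3.2.1 (deaths) and 16.2.7.4 (drug-related SAEs). It appears in 16.2.7.1, in 16.2.7.2 if severe, and possibly in the narratives planned under 14.3.3. It is in no serious-event listing.

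**6. Start of Stage 2.** SAP 6.2 puts the first Stage 2 dose on the day after the Month 36 visit. The Protocol e-diary text (Methodology and the Month 36 visit section) has dose recording start the same evening, and SAP 9.2 starts the diary on the visit day. SAP 3.6.2 assigns kits by the Stage 1 procedures, under which dosing begins that evening (SAP 3.6.1). SAP 3.8 has Stage 2 begin during the visit, and SAP 6.4 on the day of first dose after re-randomization. If the last Stage 1 dose is the evening before the visit (inferred from bedtime dosing, not stated), the day-after wording leaves visit-day events in neither window. With a same-evening first dose, the visit day is the Stage 2 first-dose date and already falls in the Stage 2 window.

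**The case against.** The strongest reply is that an on-treatment window is a coherent and common choice, stated consistently in two SAP sections, and that no section promises a by-arm table of off-drug events. That stands as a defence of having such a window. It does not justify zero lag with bedtime dosing, and it does not fill the gap in counts for children whose follow-up the Protocol links to safety.

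Several stronger readings are tempting, and the documents do not support them:
- **Off-drug safety data go unreported.** They do not. Heart rate, visual acuity, pupil size, slit lamp, fundus and intraocular pressure are summarised by visit and treatment group (SAP 9.4 to 9.9) with no stated on-drug restriction. Reasons for stopping treatment or leaving the study are counted in disposition (SAP 7.1). An event that causes a child to stop drug will usually have started by the last dose and so be in the window.
- **The SAP contradicts itself because efficacy uses all data through Month 36 regardless of treatment stopping (SAP 8.1.1).** Efficacy and adverse-event attribution may use different strategies. The contrast is informative but is not an error.
- **A post-window serious event survives only in the general listing.** The 14.3.3 narratives section covers serious events and carries no TEAE limit in its title.
- **Month 36 visit-day events belong to neither stage.** That follows only from the day-after wording in SAP 6.2.

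One limit remains. The supplied Protocol is a synopsis with a schedule, so a fuller rule on adverse-event collection after stopping drug could not be checked.

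**Conclusion.** The point holds for adverse-event reporting only. As written, the date rule misclassifies a next-morning reaction to a final dose. It also leaves events with onset after early drug discontinuation listed but without a by-arm adverse-event count: 0 of the 80 tables indexed under 14.3.1 include them. The two serious-event listings do not match the SAP text. The number of children or events cannot be derived from the documents, and a reader should not take 17% to 83% of Stage 1 as a range for the trial. The conclusion assumes that adverse events are collected at off-drug visits as the general visit text indicates, and that the SAP is followed literally. The change is worth making because it is cheap and safety is part of the primary objective. It does not bear on the primary efficacy result.

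**What to change.** 1. **Lag.** For children who stop drug early or do not continue, and after the last Stage 2 dose, extend the TEAE window in SAP 6.2 and 9.3 by at least the calendar day after the last dose. Prespecify and justify any longer lag. For children entering Stage 2, cap the Stage 1 window at the first Stage 2 dose.
2. **One descriptive table.** Show adverse events from the end of the TEAE window to the end of Stage 1, by Stage 1 treatment received (in line with SAP 5.2), with the number of children and the follow-up time at risk. Note that this is a post-randomization subset with sparser visits, and not a randomized comparison.
3. **Serious-event listings.** Make 14.3.2.2.1 and 14.3.2.2.2 cover all SAEs, with a TEAE flag.
4. **Stage 2 start.** Separately, reconcile SAP 6.2 with the Protocol e-diary text and SAP 3.6.2, 3.8, 6.4 and 9.2. Then state one rule for the stage of Month 36 visit-day events. Do not assign them to Stage 1 by default: that would reverse the SAP 6.2 convention that events on the first-dose day count as after treatment started, and could charge a reaction to a new active drop to Vehicle.

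The cost is a date-rule edit, one extra table, two relabelled listings and a little programming. No new data are needed if off-drug events are collected as described. TEAE counts would rise slightly.
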